9.2 All-cause Mortality or Cardiovascular Hospitalization

Endpoint definition: Time from randomization to the first event in this composite endpoint (i.e., time from randomization to either death or the subject's first cardiovascular hospitalization).

For subjects who have not experienced either component of this endpoint (i.e., who are censored observations), time from randomization until the subject's last follow-up contact will be used in the analysis.

The cause of hospitalization will be based on the *site-reported* data in the CABANA electronic data capture (EDC) system. For this endpoint, cardiovascular hospitalization will not include a hospitalization to initiate therapy. For example, among patients randomized to the ablation arm, the hospitalization to perform the ablation will not be counted for this secondary endpoint. Similarly, if a patient randomized to the drug arm is hospitalized to monitor the patient while loading the initial drug therapy, that hospitalization will not be counted. All other hospitalizations designated by the clinical site as *cardiovascular* will be counted, including the hospitalization of a patient randomized to the drug arm who is hospitalized for a therapy change (either a change to a different drug therapy or for crossing over to ablation). Hospitalization to perform second or subsequent ablation procedures will be counted as a CV hospitalization event.

Statistical Methods: The analysis of this secondary endpoint will use the same methods as described for the primary endpoint and key secondary endpoint in sections 8 and 9.1, including statistical testing using the log-rank test, calculation of a hazard ratio and 95% confidence interval using the Cox model, and Kaplan-Meier cumulative event rate calculations. The level of significance for the assessment of this endpoint will be $\alpha=0.05$.

9.3 All-cause Mortality, Stroke, or Hospitalization for Heart Failure or an Acute Ischemic Event

Endpoint definition: Time from randomization to the first event in this composite endpoint.

For subjects who have not experienced any component of this endpoint (i.e., censored observations), time from randomization until the subject's last follow-up contact will be used in the analysis. The stroke component of this endpoint is defined the same as the stroke component of the primary endpoint, namely as a disabling stroke characterized by a Rankin Scale ≥ 2 . The cause of hospitalization will be based on the *site-reported* data in the CABANA electronic data capture (EDC) system.

Statistical Methods: The analysis of this secondary endpoint will use the same methods as described for the primary endpoint and secondary endpoints in the sections above, including use of the log-rank test, hazard ratio and 95% confidence interval calculated using the Cox model, and Kaplan-Meier cumulative event rate calculations. The level of significance for the assessment of this endpoint will also be $\alpha=0.05$.

This endpoint is similar to the first co-primary endpoint of the Early treatment of Atrial fibrillation for Stroke prevention Trial (EAST)⁴ with the exception that EAST is using cardiovascular mortality rather than all-cause mortality as the death component of the endpoint and also a different definition of stroke (any stroke rather than a disabling stroke). Therefore, to provide results that can be compared to those of EAST, supplemental comparative analyses will be performed using cardiovascular mortality in this endpoint rather than all-cause mortality, and a definition of stroke that corresponds to the EAST definition. The statistical methods for these analyses will employ the competing risk methodology described in the next section for analyzing cardiovascular death, as well as the approach described in the preceding paragraph where all-cause mortality is a component of the endpoint.

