The complication rates of ablative intervention have been inadequately documented. While recent studies demonstrate a 1% stroke rate and a reduced PV stenosis rate down to 1-2% with ablative intervention, the same International AF Ablation Registry suggested that serious ablation events occur in up to 6% of patients [49]. The occurrence of stroke, PV stenosis, tamponade, and the recently reported lethal atrial-esophageal fistulae [53] indicate that the true complication rates of AF ablation have yet to be established.

Smaller, randomized ablation vs. drug studies include the CACAF [54], RAAFT [55], APAF [56], and A4 [57] Trials. These trials randomized 67-198 patients to rhythm control therapy vs. primary AF ablation. Over a 12-month follow-up period, a 76% average recurrence rate was seen in drug treated patients, which was greater than the 24% recurrence rate in ablated patients [54-57]. These studies also provide additional preliminary information. In the CACAF Trial [54], 1 of the ablation patients (1.5%) and one patient in the control group (1.5%) sustained a stroke, and 2 patients (3%) in the drug control group died over the course of follow-up. In the RAAFT Trial [55], re-hospitalization was required in 19 (54%) of anti-arrhythmic drug-treated patients compared with only 3 (9%) of those ablated ($p < 0.001$). No mortality was seen in either treatment group. In these studies, 20-73% of drug treated patients crossed over to ablative therapy. Since patients over the age of 75 years were largely excluded, these early trial results may not apply to the increasing elderly population of patients at risk for untoward AF-related morbidity and mortality. Nevertheless, these data show similar rates of AF elimination, all favoring ablative intervention.

At least 4 studies have assessed the outcome of catheter ablation for AF occurring in the setting of ventricular dysfunction [58-61]. In contrast to the AF CHF Trial, these studies show a substantial improvement in EF/CHF class in patients in whom sinus rhythm was restored and maintained by intervention. Accompanying data suggest that this is more likely in patients with non-ischemic than ischemic cardiomyopathy. Short follow-up periods in these studies make it impossible to draw conclusions regarding mortality and/or morbidity benefit, however.

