5.4.4 Items Left to the Discretion of the Physician

Specific items left to the investigators discretion include: 1) specific choice of rate control vs. rhythm control drug therapy and specific drugs to be used; 2) hospitalization to initiate anti-arrhythmic drug therapy; 3) choice of TEE guided direct current cardioversion (DCCV) vs. DCCV after 4 weeks of appropriate anticoagulation therapy, such as warfarin to an INR of 2-3; 4) pre-ablation TEE assessment in patients with simple paroxysmal AF and hypertension without hypertrophy; 5) continuation of warfarin to maintain a therapeutic INR at the time of catheter ablation; 6) selection of warfarin versus dabigatran, rivaroxiban or apixaban.

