7.1.2 Serious Adverse Event

An adverse event that warrants additional action, includes *any* untoward event that:

1. Is fatal
2. Is life-threatening
3. Requires inpatient hospitalization or prolongation of existing hospitalization >48 hours.
Exceptions- therefore not reportable:
 - a. Preplanned (prior to the study) hospital admissions unless the hospitalization is prolonged >48 hours beyond the anticipated length of stay.
 - b. Planned admissions (as part of a study – e.g. admission for drug change or titration for treatment of atrial fibrillation)
 - c. 23 hour hospitalizations OR observation.
 - d. Hospitalization for elective procedure (e.g. cardioversion).
 - e. Emergency room visits that do not result in hospitalization.
 - f. Hospitalization to titrate or optimize medical therapy to treat recurrence of atrial fibrillation.
4. Results in persistent or significant disability or incapacity.
5. Results in a congenital anomaly or birth defect.
6. Important medical events that may not result in death, be life-threatening, or require inpatient hospitalization may be considered an SAE when, based on appropriate medical judgment, they may jeopardize the patient and may require medical or surgical intervention to prevent one of the outcomes listed above.

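### Endpoint 2 excludes the whole therapy-initiation admission even when a cardiovascular complication prolongs it, which leans modestly towards ablation; SAP 9.9 does not say whether endpoint 9 follows the same rule

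*SAP*

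**What the plan says.** SAP 9.2 defines endpoint 2 as time from randomization to death or first cardiovascular hospitalization, with the cause of admission taken from site reports. Its general rule is that "cardiovascular hospitalization will not include a hospitalization to initiate therapy". It gives one example per arm. In the ablation arm, "among patients randomized to the ablation arm, the hospitalization to perform the ablation will not be counted for this secondary endpoint". In the drug arm, if a patient "is hospitalized to monitor the patient while loading the initial drug therapy, that hospitalization will not be counted". Every other admission that the site calls cardiovascular counts, "including the hospitalization of a patient randomized to the drug arm who is hospitalized for a therapy change". Repeat procedures count as well: "Hospitalization to perform second or subsequent ablation procedures will be counted as a CV hospitalization event". The section does not mention an initiation stay that becomes complicated or prolonged.

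SAP 9.9 (endpoint 9) analyses time to first cardiovascular hospitalization and then recurrent hospitalizations. It points to 9.2 for the composite's results. It neither repeats the exclusion nor defines a cardiovascular hospitalization itself.

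The protocol's safety section does recognise a prolonged stay. One serious-adverse-event criterion in 7.1.2 reads "Requires inpatient hospitalization or prolongation of existing hospitalization >48 hours".

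**The concern.** Leaving out a planned admission to deliver the assigned treatment is sensible. The difficulty is that the rule removes the admission whatever happens during it. A patient with tamponade during the index ablation stay who survives and stays on for two weeks has no endpoint 2 event from it. The same problem appearing a day after discharge and needing readmission is an event.

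The wording treats the arms alike, but their exposure to the rule differs. The ablation admission is part of nearly every ablation-arm patient's course and contains the procedure itself. In the drug arm, Protocol 5.4.4 leaves "hospitalization to initiate anti-arrhythmic drug therapy" to the physician, and Protocol 5.2 recommends rate control first. Complicated stays that escape counting should therefore fall mainly in the ablation arm. Endpoint 2 is tested at 0.05 in an open-label trial with site-reported causes, so a rule that leans one way should at least have its effect shown.

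**Working it through.** **Where a non-fatal index-stay complication is counted**

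- Death: endpoint 2 and the primary endpoint.
- Disabling stroke (Rankin 2 or more): the primary endpoint (SAP 8) and endpoints 3 and 5 (SAP 9.3, 9.5).
- Cardiac arrest: the primary endpoint and endpoint 6.
- Serious bleeding meeting the SAP 8 definition: the primary endpoint.
- Tamponade or perforation without death or arrest: not serious bleeding, because SAP 8 excludes bleeding with perforation or tamponade. It appears only in the adverse-event tabulation of SAP 9.12, which is mainly descriptive.
- Non-disabling stroke: outside the primary endpoint and outside endpoint 3 as defined. Only the supplemental any-stroke analysis in SAP 9.3 picks it up.

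The last two, when they prolong the index stay, enter neither the primary endpoint nor endpoint 2.

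**Size**

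The plan gives no figure to reproduce. Protocol 8.1 calls power adequate for a 25% reduction in the hospitalization composites, without a number. What follows is an illustration.

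Inputs:
- Ratio for the events the SAP counts: 0.75, from the 25% hypothesis in Protocol 2.2.2.
- Ablation-arm size: 2,204 / 2 = 1,102 (SAP introduction).
- Drug-arm cumulative risk d: assumed 30%, 50% or 70%.
- Share p of ablation-arm patients whose index stay is prolonged more than 48 hours by a cardiovascular complication: assumed 1%, 3% or 6%. The 6% comes from Protocol 1.3.1, where a registry suggested that "serious ablation events occur in up to 6% of patients".
- Prolonged drug-loading stays: assumed none. Later events are assumed independent of the index complication.

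Formulas:
- Ablation-arm risk as counted: a = 1 − (1 − d)^0.75
- Risk with complicated index stays added: a' = 1 − (1 − p)(1 − a)
- Cumulative-hazard ratio: ln(1 − a') / ln(1 − d) = 0.75 + ln(1 − p) / ln(1 − d)

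Example, d = 50% and p = 3%: 0.75 + (−0.0305)/(−0.6931) = 0.75 + 0.044 = 0.794.

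| Share p (patients of 1,102) | d = 30% | d = 50% | d = 70% |
|---|---|---|---|
| 1% (11) | 0.778 | 0.764 | 0.758 |
| 3% (33) | 0.835 | 0.794 | 0.775 |
| 6% (66) | 0.923 | 0.839 | 0.801 |

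The only hospitalization rates in the documents are 73.0% and 80.1% rehospitalization in the large rate-versus-rhythm trial (Protocol 1.2.4). They are not limited to cardiovascular causes, so they are an upper guide to d. At those values the ratio is about 0.76 for p = 1%, 0.77 for 3% and 0.79-0.80 for 6%.

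**Endpoint 9**

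There are two readings of SAP 9.9. If the 9.2 exclusion does not carry over, every index ablation admission that a site calls cardiovascular is an event, which can hardly be intended. If it does carry over, the same gap applies, including in the recurrent-event analysis. The text does not settle which.

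**The case against.** The strongest reply is that endpoint 2 counts admissions. A longer planned stay is not a new admission, so counting it is a choice of estimand. Resource use is a separate endpoint (10) with its own analysis plan. That stands, and it is why the 9.2 definition need not change.

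A reader might infer that ablation's main in-hospital harm drops out of both hospitalization endpoints. The documents do not support this. The exclusion is worded for endpoint 2 only, and 9.9 is silent. Index-stay deaths count in endpoint 2, the gravest non-fatal events count in the primary endpoint, procedural harms are named in 9.12, and later cardiovascular readmissions count. That 9.2 drops complicated stays is the effect of an unqualified rule; the SAP does not state it as an intention.

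The large shifts also need care. The 6% covers all serious ablation events, so it overstates those that are cardiovascular and prolong the index stay. The 0.92 pairs it with the lowest assumed drug-arm risk.

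Finally, no document says how often drug patients are admitted to start therapy, and proarrhythmia is a named drug-arm harm, so some offset is possible. The lean towards ablation is a reasonable expectation from the care pathway, not a measured fact. In the pilot, 28 of 29 patients randomized to ablation had the procedure (Protocol 1.3.2).

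**Conclusion.** The point holds in limited form. SAP 9.2 does not deal with an initiation stay prolonged by a cardiovascular complication. Read as written, it drops such stays from endpoint 2, mainly in the ablation arm, and SAP 9.9 leaves its own definition open. The lean is modest: from 0.75 to about 0.76-0.84 if 1-3% of index stays are affected, with 0.80-0.92 at 6% as a ceiling. These figures assume a ratio of 0.75 for counted events, drug-arm risk of 30-70%, no prolonged drug-loading stays and independence of later events. They are cumulative-hazard ratios, not forecasts of the Cox estimate. A supplementary analysis and a clarified definition are warranted; a new definition of endpoint 2 is not.

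**What to change.** 1. Keep the SAP 9.2 definition for the main analysis of endpoint 2.
2. State in SAP 9.9 whether the 9.2 definition of a cardiovascular hospitalization applies, for both the first-event and the recurrent-event analyses.
3. Add a named supplementary intention-to-treat analysis of endpoints 2 and 9. In it, an initiation admission in either arm (index ablation or initial drug loading) counts as a cardiovascular hospitalization, dated at the complication, when a cardiovascular adverse event prolongs it by more than 48 hours.
4. Specify how prolongation is identified, in the same way for both arms. The serious-adverse-event field may not be enough. Protocol 7.1.2 merges new admission with prolongation. It also exempts planned study admissions, with drug titration as its example, without the prolongation proviso that it attaches to preplanned ones. Some prolonged drug-loading stays might otherwise go unflagged.

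The cost is a few lines of SAP text and a little extra derivation; whether existing fields suffice needs checking against the case report form. Prolongation would be reported by unblinded sites, and the supplementary result may be less favourable to ablation.

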9.4 Cardiovascular Death

Endpoint definition: Time from randomization to the occurrence of a cardiovascular (CV) death.

Patient deaths will be classified by the Clinical Events Committee (CEC) as to whether the mode of death was due to a cardiovascular (CV) cause. If insufficient source documents are obtained to allow CEC adjudication of the cause of death, and the CEC classifies the cause of death as "unknown," then the site-reported cause of death (if available) will be used. If neither the site nor the CEC can provide a classification of the cause of death, the death will not be considered as a cardiovascular death. As supplemental analyses, however, this endpoint will also be examined using (a) only the deaths classified by the CEC as cardiovascular, and (b) using deaths

classified by the CEC as cardiovascular, but also including any deaths in the cardiovascular category that are classified as unknown by the CEC.

Statistical Methods: The analysis of this endpoint will be performed using the competing risks methodology of Fine and Gray⁵, where death due to a non-cardiovascular cause is considered as a competing risk. This methodology, rather than treating non-cardiovascular death as a censoring event, makes use of the cumulative incidence function, and is performed within the proportional hazards framework using the marginal failure sub-distribution associated with the event of interest (cardiovascular death). The features of the Fine-Gray approach for handling competing risks data are available as part of the PHREG procedure in SAS. The cumulative incidence function for the two arms will be estimated, statistically compared, and graphically presented using the PHREG software features in SAS. For subjects who have not died, time from randomization until the subject's last follow-up contact will be used in the analysis. The level of significance for the assessment of this endpoint will be $\alpha=0.05$.

Additional analysis of this secondary endpoint will be performed using the same methods as described for the primary endpoint and secondary endpoints in the sections above, including use of the log-rank test, hazard ratio and 95% confidence interval generated using the Cox model, and Kaplan-Meier cumulative event rate calculations. Patients who have died but whose cause of death is classified by the CEC as non-cardiovascular will be censored at the time of their non-CV death. The number of such patients is expected to be relatively small in this study. The results of these two different approaches will be carefully examined and synthesized into an overall interpretation of treatment differences with respect to CV death.

9.5 Cardiovascular Death or Disabling Stroke

Endpoint definition: Time from randomization to the occurrence of either a cardiovascular death or disabling stroke.

All potential strokes will be carefully reviewed and classified as disabling by the neurological events committee using the Rankin Stroke Scale as described in Section 8. The neurological committee that reviews and adjudicates the strokes is an important part of the overall clinical events adjudication process. A disabling stroke will be defined as a stroke whose severity on the Rankin Scale is ≥ 2 . Cardiovascular deaths will be classified as described in Section 9.4 above.

Statistical Methods: The analysis of this secondary endpoint will also use the competing risks methodology of Fine and Gray⁵ described in Section 9.4 for the secondary endpoint of CV death where death due to a non-cardiovascular cause is considered as a competing risk rather than a censoring event. The analysis will make use of the cumulative incidence function, and (as described in Section 9.4) will be performed within the proportional hazards framework using the marginal failure sub-distribution associated with the event of interest. The cumulative incidence function for the two arms will be estimated, statistically compared, and graphically presented using the PHREG procedure in SAS. For subjects who have not died, time from randomization until the subject's last follow-up contact will be used in the analysis. The level of significance for the assessment of this endpoint will be $\alpha=0.05$.

As in the case of the cardiovascular death endpoint, additional analysis of this secondary endpoint will be performed using the log-rank test, hazard ratio and 95% confidence interval generated using the Cox model, and Kaplan-Meier cumulative event rate calculations. Patients who have died but whose cause of death is classified by the CEC as non-cardiovascular will be censored at the time of their non-CV death. Results of these two different approaches will be carefully compared and synthesized into an overall interpretation of treatment differences with respect to the endpoint of CV death or disabling stroke.

9.6 Arrhythmic Death or Cardiac Arrest

Endpoint definition: Time from randomization to the occurrence of either an arrhythmic death or cardiac arrest.

Since cardiac arrest is a component of the primary endpoint, all potential cardiac arrests will be reviewed and adjudicated by the Clinical Endpoints Committee. As described earlier, the mode of death is also classified by the Clinical Endpoints Committee.

Statistical Methods: The analysis of this secondary endpoint will proceed in much the same way as described above for the endpoint of CV death or disabling stroke and use the competing risks methodology of Fine and Gray⁵ described in previous sections. In this analysis, death due to a cause other than arrhythmic is considered as a competing risk rather than a censoring event. The analysis will make use of the cumulative incidence function, and will be performed within the proportional hazards framework using the marginal failure sub-distribution associated with the event of interest. The cumulative incidence function for the two arms will be estimated, statistically compared, and graphically presented using the features available in the PHREG procedure in SAS. For subjects who have not died, time from randomization until the subject's last follow-up contact will be used in the analysis. The level of significance for the assessment of this endpoint will be $\alpha=0.05$.

For this endpoint, we will also perform additional analysis using the log-rank test, hazard ratio and 95% confidence interval generated using the Cox model, and Kaplan-Meier cumulative event rate calculations. Patients who have died but whose cause of death is classified by the CEC as other than arrhythmic will be censored at the time of the non-arrhythmic death. The results of these two different approaches will be compared and synthesized into an overall interpretation of treatment differences with respect to the endpoint of arrhythmic death or cardiac arrest.

9.7 Heart Failure Death

Endpoint definition: Time from randomization to the occurrence of a heart failure death.

Classification of deaths as being due to heart failure will be performed by the blinded Clinical Endpoints Committee.

Statistical Methods: The analysis of this endpoint will make use of the competing risks methodology of Fine and Gray⁵ described in previous sections for other secondary endpoints. In this case, death due to a cause other than heart failure will be considered as a competing risk. The

features of the Fine-Gray approach for handling competing risks data available as part of the PHREG procedure in SAS will be employed to estimate the cumulative incidence function for each of the two arms, to statistically compare these functions, and graphically present them using the software features in SAS. The level of significance for the assessment of this endpoint will also be $\alpha=0.05$.

Additional analysis of this secondary endpoint will also be performed using the log-rank test, hazard ratio and 95% confidence interval (CI) generated using the Cox model, and Kaplan-Meier cumulative event rate calculations. For this analysis, patients who have died, but their death is classified by the CEC as due to a cause other than heart failure, will be censored at the time of their non-heart failure death. The results of the competing risk analysis and of this traditional analysis will be compared to synthesize an overall interpretation of the treatment differences.

